STUDY PROTOCOL
May 1, 2017

Project Title: Integrating Safer Conception Counseling to Transform HIV Family Planning Services

NCT03167879

Registered on clinicaltrials.gov on 5/23/17

STUDY PROTOCOL

Overview. This 3-arm, cluster RCT will compare two models for implementing a comprehensive FP program that integrates SCC within current FP services in HIV clinics—an up to 6-session, multi-component, structured SCC intervention (SCC1), and a workshop to train FP providers on use of SCC guidelines (SCC2)—versus existing FP services (usual care). Both SCC1 and SCC2 will use routine screening for fertility desires and a workshop for training FP nurses to implement SCC, but SCC1 is differentiated by its use of a structured counseling SCC protocol and manual (as opposed to the clinical acumen of the trained FP nurses), and inclusion of client outreach and ongoing supervision support. Each arm will be implemented at 2 sites (6 sites in total) and each site will enroll 65 clients (total n=390) with serodiscordant partners who have childbearing desires at recruitment. Participants will be surveyed at baseline, months 6 and 12, and post-pregnancy for those who become pregnant prior to month 12. The primary outcome is correct use of SCM or contraception (depending on desired pregnancy status following SCC consult); secondary outcomes are pregnancy status, PMTCT use (if pregnant), partner seroconversion, and condom use. A cost-effectiveness analysis will also compare the 3 arms to inform policy and practice recommendations for settings of various resource levels.

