Routinely collected clinic data will be used to analyze FP services in the overall clinic population to examine clinic capacity and fidelity to the intervention. The triage book and childbearing screening item (in SCC1/SCC2 sites) will be used to determine: (a) # who do not want children and % receiving contraception services, and (b) # reporting childbearing desires. FP registries will indicate # new clients receiving FP services (not seen by FP in past year), and % of FP recipients using dual contraception. These will be tracked longitudinally to assess intervention effects on clinic level FP services. % of clients receiving FP referrals after triage will be compared across all 3 arms using research cohort data, since childbearing screening is not used at the usual care site.

Research Participants. The assigned FP programs at each study site will be implemented clinic-wide for all clinic clients, but the 66 study clients enrolled at each site will meet the following **eligibility criteria**:

1. Adults of reproductive age (men age 18-60; women age 18-45).
2. Considering childbearing with their spouse/partner. This will be determined via the triage screening item.
3. Reports having disclosed HIV status to partner. TASO counselors provide clients with assisted disclosure services to help them disclose to partners. Therefore, interested clients who have not yet disclosed their HIV status to their partner will be assisted to do so if they wish, after which they can be considered for enrollment.
4. Partner is HIV-negative. All couples can benefit from SCC and FP, but we focus on discordant couples due to the heightened value of SCC for reducing horizontal HIV transmission. We will use a rapid HIV test to confirm partner's status, and offer the option of a home-based test (a service offered by TASO) if necessary. Confirming the partner's status enables us to accurately assess intervention effects on seroconversion.

ART use is not an eligibility criterion, but SCC will be used to advise and support clients to start and adhere to ART before trying to conceive with SCM. TASO provides ART to all clients in serodiscordant relationships.

Note that only the HIV+ client will enroll in the study and participate in the survey research, not their partners.

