Recruitment. We will enroll 3-4 clients per month over 18 months at each site, which is feasible as >20 clients met this eligibility criteria in each recruitment month in our pilots. Recruitment will be stratified by sex to ensure a 50/50 gender balance, which will better enable us to examine intervention effects on partner seroconversion

and to gain the perspective of both male and female clients regarding fertility. We could enroll the sample more quickly, but the long enrollment period ensures we can recruit the target number of men, and enables us to have our 3 site coordinators manage three sites each (min. 1 day per week at each clinic) to limit personnel costs. Clients at the SCC1 and SCC2 sites who report at triage that they desire to have a child with a negative or unknown HIV status partner will be referred by triage to the site coordinator for screening. Screening (incl. partner HIV testing) and baseline survey will be completed prior to the initial SCC consultation. At the usual care site, the childbearing screening item will be included at triage only during the days of recruitment, which will be used to identify potential participants who will then be referred to the site coordinator for the same screening conducted at the intervention sites; the data from the screening item will not be placed in the client's chart or given to the FP nurse, as this screening is not part of usual care. Clients who decline to bring their partner in for HIV testing (but are otherwise eligible) and thus do not participate, will be asked to provide basic sociodemographic and partner characteristics in order to assess how they differ from the enrolled clients.

Data Collection

Assessment schedule: The baseline assessment will be done by the site coordinator once eligibility is confirmed, followed by assessments at months 6, 12, and post-pregnancy (if pregnancy occurs prior to month 12). To minimize attrition we will collect contact info (phone numbers and maps of homes), including contact information for family or friends who have frequent contact with the client. Clinic staff will also be able to help us track clients that we have difficulty reaching. In our current study we achieved 94% retention at Month 12.

Participant Compensation: Participants will receive 20,000 Ush (~\$6 USD) at each assessment.

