Power analysis: 11% of PLHA in Uganda who want to prevent pregnancy use dual contraception³⁰ and our research shows 15% of PLHA trying to conceive use TUI or MSI.³⁷ Therefore, we expect the usual care arm will have a 15% rate of correct use of contraception/SCM (depending on pregnancy intentions), which is the primary outcome. Using an intra-class correlation (ICC) of 0.01 to control for clustering, based on other studies of reproductive health outcomes,⁷⁴ and 10% attrition at Month 12 (given the 6% in our current study), we will have > 80% power (2-tailed test) to detect a 4.5 percentage point difference (small effect size; $d=.15$) for our comparison of the usual care arm to the combined SCC1 & SCC2 arms on the use of contraception or SCM at month 12, and a 7-8 percentage point difference between the SCC1 and SCC2 intervention arms. In analysis of effects on contraception and SCM use separately, and with half the sample expected to decide to pursue pregnancy and half contraception based on our pilot data, our sample size will provide > 80% power to detect a 6.5 percentage point difference with regards to each of the outcomes when comparing usual care to SCC1 and SCC2 combined, and 8-9 percentage point difference between the SCC1 and SCC2 interventions.

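### The stated power (>80% for a 4.5-point difference) does not follow from the plan's own inputs, which give about 12% power and a detectable difference of about 17 points

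*Combined protocol and SAP*

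**What the plan says.** The Power analysis paragraph of the Data Analysis Plan expects 15% correct use under usual care. It rests this on two sources: "11% of PLHA in Uganda who want to prevent pregnancy use dual contraception", and a 15% rate of TUI or MSI use among those trying to conceive. It then allows for clustering ("Using an intra-class correlation (ICC) of 0.01 to control for clustering") and for 10% attrition at month 12. From these inputs it makes four claims, all at more than 80% power:

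- Usual care vs SCC1 and SCC2 combined: "> 80% power (2-tailed test) to detect a 4.5 percentage point difference", described as a small effect with d = 0.15.
- SCC1 vs SCC2: "a 7-8 percentage point difference between the SCC1 and SCC2 intervention arms".
- Contraception and SCM use analysed separately, with half the sample in each, combined arms vs usual care: "power to detect a 6.5 percentage point difference with regards to each of the outcomes".
- The same separate analyses, SCC1 vs SCC2: 8-9 points.

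The Overview gives the size: "Each arm will be implemented at 2 sites (6 sites in total) and each site will enroll 65 clients (total n=390". Other sections disagree with it. Research Participants has "the 66 study clients enrolled at each site". Recruitment plans to "have our 3 site coordinators manage three sites each", which implies nine sites. The Data analysis paragraph and Aim 3 both refer to nine clinics. No alpha level is stated.

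**The concern.** A 4.5-point difference from a 15% base is small. About 350 evaluable clients, split 1:2 and clustered in six clinics, would not be expected to detect it reliably.

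This is the power statement for the primary comparison, and the SCC1 vs SCC2 figure supports the choice between a more and a less intensive model. A reader who trusts the paragraph would take a non-significant primary result as evidence against effects of 5 points or more. The same reader could take a non-significant SCC1 vs SCC2 result as near-equivalence and favour the cheaper model. If the true detectable differences are several times larger, neither reading is justified.

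**Working it through.** **Inputs.** From the Power analysis paragraph: usual-care rate 15%, ICC 0.01, attrition 10%, two-tailed test, stated difference 4.5 points (15% vs 19.5%). From the Overview: two clinics per arm, 65 clients per clinic, so 130 usual care and 260 combined SCC. Assumed: alpha 0.05.

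**Effective sample size.**
- Evaluable per clinic: 65 × 0.9 = 58.5, so 117 vs 234.
- Design effect: 1 + (58.5 − 1) × 0.01 = 1.575.
- Effective n: 117 / 1.575 = 74.3 and 234 / 1.575 = 148.6.

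**Power at the stated difference** (two-proportion z-test, pooled SE under the null, unpooled under the alternative).
- Pooled rate: (0.15 + 2 × 0.195) / 3 = 0.18.
- Null SE: √[0.18 × 0.82 × (1/74.3 + 1/148.6)] = 0.0546.
- Alternative SE: √[0.15 × 0.85/74.3 + 0.195 × 0.805/148.6] = 0.0527.
- (0.045 − 1.96 × 0.0546) / 0.0527 = −1.18, so power is about 12%. Unpooled and arcsine versions give 13-14%.

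**Difference detectable at 80% power.** Solving the same expression gives 17.0 points. Check at 15% vs 32%: null SE 0.0626, alternative SE 0.0564, (0.17 − 1.96 × 0.0626) / 0.0564 = 0.84, power 80%. Unpooled and arcsine versions give 15.7 and 16.6 points.

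**Can the stated figure be reproduced?** No variant tried reaches 80%:

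| Setting | Power at 4.5 points | Detectable at 80% |
|---|---|---|
| 6 × 65, 10% attrition, ICC 0.01 | 12% | 17.0 points |
| 6 × 65, 10% attrition, ICC 0 | 17% | 13.2 |
| 6 × 65, no attrition, ICC 0 | 18% | 12.4 |
| 9 × 66, 10% attrition, ICC 0.01 | 16% | 13.5 |
| 9 × 66, 10% attrition, ICC 0 | 24% | 10.4 |
| 9 × 66, no attrition, ICC 0 | 26% | 9.8 |

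For 6 × 65 with ICC 0.01, alpha 0.10 gives about 20%, and testing d = 0.15 as a difference of two means gives 18%. The most favourable combination tried (9 × 66, no clustering, no attrition, one-sided, d = 0.15) reaches 53%.

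Without clustering, 80% power at 4.5 points needs about 840 + 1,680 = 2,520 evaluable clients. The plan has 351, and 2,520 / 351 = 7.2.

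**Companion figures**, same method. The separate analyses assume half of each clinic: 29.25 per clinic, design effect 1 + 28.25 × 0.01 = 1.2825, effective n 58.5 / 1.2825 = 45.6 per arm (91.2 for the combined arms).

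| Comparison | Stated | Base rate | Power at stated | Detectable, 6 × 65 | Detectable, 9 × 66 |
|---|---|---|---|---|---|
| SCC1 vs SCC2 | 7-8 | 15% / 19.5% | 17-24% | 19.7 / 20.9 | 15.6 / 16.7 |
| Separate outcomes, combined vs usual care | 6.5 | 11% / 15% | 15% / 14% | 21.1 / 22.4 | 16.4 / 17.7 |
| Separate outcomes, SCC1 vs SCC2 | 8-9 | 11% / 15% | 16-22% | 24.5 / 26.0 | 19.1 / 20.5 |

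**Simulation check** (beta-binomial, 20,000 runs, 2 vs 4 clinics of 58, ICC 0.01). The cluster-adjusted test had power 0.119 at 4.5 points, 0.398 at 10 and 0.802 at 17. The same test without adjustment rejected 11% of the time when there was no effect.

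**Effect size.** For 15% vs 19.5%, arcsine h is 0.12 and 0.045 / √(0.15 × 0.85) is 0.13. Logit and probit conversions give about 0.175 and 0.18. None of these gives 0.15.

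**The case against.** - **The effect may be large.** The plan gives a detectable difference, not an expected one, and calls the study a proof of concept. This stands: the documents do not show the trial is underpowered for the effect its authors expect. They do show that its sensitivity is misstated.
- **The planned analysis may be more sensitive than a design-effect-adjusted z-test.** The main model is covariate-adjusted logistic regression with no cluster adjustment in its main fit, followed by a sensitivity analysis over ICC values. But with no clustering at all, power is still 17% and the detectable difference about 13 points. The power paragraph takes no credit for covariates, and their gain could not reasonably close a sevenfold shortfall. Where clustering exists, an unadjusted test also has an inflated false-positive rate.
- **The size of the error depends on the clinic count.** This stands. The factor of 2.5 to 4 is for six clinics; with nine clinics of 66 it is about 2 to 3.
- **The d = 0.15 mismatch is minor.** This is fair. The plan names no convention, and 0.15 lies between the values that common conventions give.
- **The separate SCC1 vs SCC2 figures use usual-care base rates for SCC2.** Raising them by the plan's own 6.5 points moves 24.5 and 26 to about 27 and 28, further from the stated 8-9.

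The recomputation is, if anything, lenient. It uses a normal reference and leaves out the attrition-weight design effect that the plan says it will incorporate. With a t reference on 4 degrees of freedom, power is 10% and the detectable difference 21.5 points.

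**Conclusion.** The concern holds. For the primary comparison, the plan's inputs give about 12% power at 4.5 points, not more than 80%, and about 17 points detectable at 80% power. The other three figures are wrong in the same direction. Neither the ICC, the variance formula, the unstated alpha nor the conflict between six and nine clinics accounts for the gap.

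With six clinics, effects below about 9 points would more likely than not be missed even with no clustering. A 10-point effect has about 58% power with no clustering and about 39% at ICC 0.01.

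The result rests on alpha 0.05 two-sided and, for the separate outcomes, on half of each clinic entering each analysis. The error lies in the claimed sensitivity; it does not bias the estimates. It must be fixed because it governs what a null result may be taken to exclude.

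**What to change.** Keep the sample. First settle the number of clinics (six or nine) and the clients per site (65 or 66) throughout the document. Then restate all four figures with alpha, method, base rates and cluster count, and delete d = 0.15. For six clinics of 65, suitable text would be:

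> With two-sided alpha 0.05, ICC 0.01, 10% attrition and a design-effect-adjusted two-proportion test with a normal reference, 80% power is available for about 17 points (15% vs 32%; arcsine h about 0.4) for combined SCC vs usual care, and about 20-21 points for SCC1 vs SCC2 (SCC2 rate 15% to 19.5%). With half the sample per component, the figures are about 21 points (contraception, 11% base) and 22 points (SCM, 15% base) for combined SCC vs usual care, and about 24.5 and 26 points for SCC1 vs SCC2 at the same base rates. A non-significant result, including SCC1 vs SCC2, does not rule out effects smaller than these.

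If the last pair assumes SCC2 rates 6.5 points above usual care, use about 27 and 28. If the design is nine clinics of 66, the four figures become about 13.5, 16-17, 16-18 and 19-20.5 points.

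The cost is a rewrite of the power paragraph and a much less favourable statement of sensitivity. No participants are added, and the analysis does not change.

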Tools will be developed to facilitate SCC [session checklists, posters for the waiting and clinician rooms, pregnancy planning calendar, client SCM kits (needleless syringe, plastic cup, non-spermicidal condoms, lubricant), client pictorial instruction brochures (see appendix) and video demonstrations]. Guided by our consultant, [name], who has been using brief, simple SCM instructional videos created for use on Youtube by videotaping counseling role plays and testimonials of successful couples, we will create video clips for use in training FP nurses as well as to be used by the nurses to train clients, and for clients to refer to at home or where they can access the internet. These low cost videos can be made quickly and will be made using nurse role plays at first, but we will engage actual clients (with consent) who use the services over time. We will be particularly keen to engage male clients/partners in videos, as a way to foster male involvement.

(3) Routine screening of childbearing desires: To ensure clients receive either SCC or contraception as needed, a single question, “Are you thinking about trying to conceive a child within the next 12 months?” will be asked by expert clients at the triage station (which is where clients go after checking in for their visit) for all reproductive aged men (age 18-60) and women (age 18-45). The screening item is liberally worded so that it is inclusive of clients who are considering childbearing but may not be certain about their own desire or that of their partner, which will enable more clients to receive support from SCC to make an informed decision. Clients who report childbearing desires will be seen by a trained FP nurse for a SCC consult during the same clinic visit or scheduled for a future visit if the client is willing and able to bring their partner in for the consult. If the client is interested in participating in the study, the partner will need to come in for HIV testing prior to receiving the first SCC consult. Clients with no childbearing desires will be seen by the FP nurse for contraception.

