(4) Structured (up to 6) monthly SCC sessions: Sessions will follow a structured protocol and the manual used in the pilots (see appendix), which we will adapt to include linkage to the clinic's contraception services for a more comprehensive FP program. The first consult focuses on: the client's relationship context; the client's health, review of risks and benefits related to childbearing and need for any medical treatments prior to conception; and fertility desires of both the client and partner and the need for a joint agreement to be reached. This will help the couple make an informed decision about childbearing, and determine whether SCC or contraception services are needed; contraception will be recommended until a joint agreement on childbearing is reached. This joint decision process can be aided by SCC even in the absence of the partner, as shown in the pilot where many clients decided against childbearing after discussing with their partner after the consult.

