This model for integrating SCC into existing FP services mimics the approach used by the MoH for infusing new services. Like SCC1, SCC2 will also use screening of childbearing desires and clients who report such desires will be encouraged to discuss this with their providers, and the triage station will record the information in the client's chart so that providers can refer the client to the FP nurses for SCC or contraception. Training of FP nurses (see Fig. 2) will be mostly educational and use role plays, but will not train on use of MI style communication with clients. A simplified manual and some (SCM instructional brochures, fertility calendar) but not all tools (instructional videos; SCM kits) produced for SCC1 will be used in SCC2. Supervision will not be provided by the study supervisors; rather, FP nurses may consult with clinic physicians and the FP clinic on the hospital campus when needed, which is the typical approach for new services. Like SCC1, SCC2 sessions will be recorded and a random selection coded for fidelity by the Project Director, but feedback will not be given to the nurses, as this is not the norm when new services are added. SCC2 is designed to reflect how new treatment advances are integrated into routine care by the MoH, and to represent a viable, less intensive alternative to the structured, multi-component SCC1, the comparison of which provides critical data to guide the MoH and other policy makers on how to best incorporate SCC into FP services. SCC sessions attended by participants will be logged and research participant surveys will assess SCC and FP services received.

Arm 3: Existing FP services (usual care control) Each study site currently provides FP services that focus on providing contraception and PMTCT care, but there's no SCC. The usual care sites will continue to provide FP services as is, with no use of routine screening of childbearing desires or SCC. Routine HIV and FP care in Uganda is unlikely to incorporate SCC during the course of this study, as SCC guidelines have been available

for years, yet SCC has remained scarce in Uganda and SSA. Also, TASO has indicated it has no plans to integrate SCC into usual care until the study ends and it sees efficacy and cost-effectiveness data.

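### The separate SCM and contraception comparisons appear to be restricted by a pregnancy decision that SCC is meant to inform, and their stated power is not reproduced by the plan's own inputs

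*Combined protocol and SAP*

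**What the plan says.** The primary outcome is one binary indicator of correct SCM or contraception use, "depending on desired pregnancy status following SCC consult" (Overview). Besides this composite, the Power analysis section describes separate analyses of the two behaviours, "with half the sample expected to decide to pursue pregnancy and half contraception based on our pilot data". For each it states more than 80% power to detect 6.5 percentage points between usual care and the two SCC arms combined, and 8-9 points between SCC1 and SCC2.

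On how the split arises:

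- Eligibility criterion 2 (Research Participants) requires every client to be "Considering childbearing with their spouse/partner". The screening item is worded to be "inclusive of clients who are considering childbearing but may not be certain about their own desire" (Arm 1, item 3).
- At the SCC sites the "baseline survey will be completed prior to the initial SCC consultation" (Recruitment), so the decision that defines the subgroups comes later.
- The first consult is intended to help the couple decide about childbearing. In the pilot, "many clients decided against childbearing after discussing with their partner after the consult" (Arm 1, item 4).
- Usual-care sites continue as they are, "with no use of routine screening of childbearing desires or SCC" (Arm 3).

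The Data analysis section and Aims 1 and 2 give no analysis set for the separate comparisons. Intent-to-treat is stated for the primary analyses, and the planned covariates are baseline variables.

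**The concern.** If SCM use is compared only among clients who pursue pregnancy, and contraception only among the rest, the comparison conditions on something that happens after assignment and that SCC can change. Suppose the consult leads some couples not to pursue pregnancy, and those couples would have been poor SCM users. Removing them raises the SCM rate among the remaining pursuers without anyone using SCM better. If they would have been good SCM users, the rate falls. The contraception group changes in the same way. Baseline covariates can reduce this selection but do not in general remove it.

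The trial is meant to guide the health ministry on how to add SCC to family planning services, so a subgroup rate could be read as evidence that SCC improves one particular method. The power statement adds to the risk, because it presents these comparisons as able to detect modest effects.

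**Working it through.** **1. Is the denominator really restricted?** The plan does not say so outright, but three features point that way.

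- A half-and-half split would not affect sample size if all clients stayed in both denominators.
- The detectable difference rises from 4.5 points (composite) to 6.5 (separate). The ratio is 6.5/4.5 = 1.44, close to √2 = 1.41, as halved denominators would give.
- The base rates are conditional: 11% dual contraception among those wanting to prevent pregnancy, and 15% TUI or MSI use among those trying to conceive.

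**2. The plan's power figure.** Inputs from the Overview and Power analysis: 65 clients per site, 2 sites per arm, 10% attrition, half the sample, ICC 0.01, two-tailed test. Alpha is not stated; 0.05 is assumed.

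- Completers per site in one subgroup: 65 × 0.9 / 2 = 29.25.
- Design effect: 1 + (29.25 − 1) × 0.01 = 1.2825.
- Effective n: usual care 2 × 29.25 / 1.2825 = 45.6; SCC combined 91.2.
- Power = Φ[(d − 1.96·SE₀)/SE₁] plus the negligible opposite tail, with SE₀ pooled and SE₁ unpooled.
- SCM, 15% v 21.5%: SE₀ = 0.0716, SE₁ = 0.0682; (0.065 − 0.1404)/0.0682 = −1.11; power 0.136.
- Contraception, 11% v 17.5%: SE₀ = 0.0653, SE₁ = 0.0611; (0.065 − 0.1281)/0.0611 = −1.03; power 0.152.
- Difference needed for 80% power: 22.4 points (SCM) and 21.1 points (contraception).

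The stated figure of more than 80% is not reproduced. Ignoring clustering gives only 16% and 19%. The Data analysis section and Aim 3 mention 9 clinics; at 3 per arm and 65 each, power is 19% and 21%.

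SCC1 v SCC2 has effective n of 45.6 per arm. The SCC2 rate is not given, so I took 11% to 21.5%. Power for 8.5-9 points is then about 15-22%, and 80% power needs about 24-28 points.

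**3. How large could the artefact be?** The documents give no usual-care split, so this is illustration. Let u be the share pursuing pregnancy under usual care, with 50% pursuing under SCC. Switchers are clients who would pursue under usual care but not under SCC. Every client type's use, given intention, is the same in all arms. Usual-care pursuers use SCM correctly at 15%, and switchers at r × 15%.

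SCM rate among SCC pursuers = [0.15u − 0.15r(u − 0.5)] / 0.5. The artefact is this minus 0.15.

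| u | r = 0 | r = 0.5 | r = 1 | r = 1.5 |
|---|---|---|---|---|
| 0.5 | 0 | 0 | 0 | 0 |
| 0.6 | +3.0 | +1.5 | 0 | −1.5 |
| 0.7 | +6.0 | +3.0 | 0 | −3.0 |
| 0.8 | +9.0 | +4.5 | 0 | −4.5 |
| 0.9 | +12.0 | +6.0 | 0 | −6.0 |

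(Percentage points.) For example, u = 0.8 and r = 0 give 0.15 × 0.8 / 0.5 = 0.24, which is +9 points.

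For contraception, with base rate 11% and switcher rate s, the artefact is [0.11(1 − u) + s(u − 0.5)] / 0.5 − 0.11. Over u = 0.6 to 0.9 it is −2.2 to −8.8 points at s = 0, zero at s = 11%, and +1.8 to +7.2 at s = 20%.

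**The case against.** The strongest reply is that these comparisons are barely in the plan. They appear in one sentence of the Power analysis section. The primary analysis and Aim 1 use the composite, and the secondary outcomes list no separate SCM or contraception rate. That stands: the denominator is an inference and the results are supplementary. But the sentence makes a power claim for the comparisons, and nothing later gives them a different analysis set.

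The artefact sizes are also assumption throughout, and this stands too. The plan gives a single 50/50 split for the whole sample, at which the artefact is zero. Usual care already offers contraception and the screening item admits uncertain clients, so usual-care clients may also decide against childbearing. A reader might infer from the pilot remark that SCC lowers the share pursuing pregnancy, or that the bias favours SCC. The remark has no comparator and no percentage, so it supports neither. A reader might also infer a high false-positive rate. At the extreme (u = 0.9, r = 0) the chance of p < 0.05 is about 60% with clustering ignored, or about 47% with a test corrected at ICC 0.01; both rest on invented inputs.

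It could be argued that SCC1 versus SCC2 is safe because both arms counsel. The documents do not support that. The decision-making consult and the pilot remark are described under SCC1, while SCC2 has a simplified manual, shorter training and no study supervision.

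Finally, the power shortfall is independent of the conditioning problem and adds no weight to it.

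**Conclusion.** The concern holds in limited form. The separate comparisons appear to condition on a post-assignment decision that SCC is designed to inform, so a subgroup difference from usual care cannot by itself be read as better or worse use of a method. SCC1 versus SCC2 may be affected as well. Size and direction are unknown; the range of −6 to +12 points for SCM depends wholly on the assumed splits and switcher rates.

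A reader might extend this to the primary outcome. That would go too far: the composite counts every client, so it does not have this denominator problem, although a shift in decisions can still move its value.

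The power finding is firmer, resting on the plan's inputs and an assumed alpha of 0.05. Power is about 14% and 15% for 6.5 points, and about 15-22% for 8.5-9 points between the SCC arms (SCC2 rates of 11-21.5% assumed), against more than 80% stated. The point deserves correction before analysis but does not threaten the primary comparison's validity.

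**What to change.** 1. In the Power analysis and Data analysis sections, state that SCM and contraception rates restricted by pregnancy decision are descriptive; that they are reported beside the proportion intending pregnancy in each arm at months 6 and 12; and that they do not support a claim that SCC improved a specific method. Between-arm inference rests on the composite primary outcome among all enrolled clients.
2. Remove the claims of more than 80% power for 6.5 and 8-9 points, or restate them with the recomputed figures and every input.
3. Optionally, add one supportive binary logistic model per method among all enrolled clients by assigned arm: success through correct SCM (yes/no) and success through correct contraception (yes/no). Define in advance how clients who conceive before the six-month look-back window are counted.

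The optional models have limits. About 18 usual-care successes are expected in total (15% of 117 completers). The all-enrolled shares also move when decisions shift: in the illustration SCM changes by −0.15r(u − 0.5), from 0 to −9 points, and contraception by s(u − 0.5), from 0 to +8. They must be read with the intention proportions and do not isolate which method improved.

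The cost is SAP wording and one table, since intentions and method use are already collected. The trial gives up method-specific claims from subgroups, and its stated power becomes less favourable.
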